1.14 ARIA-Related Interventions Including Dose Changes and Discontinuation

See main protocol Sections 3.6, 6.1.15, and 6.1.16 for details of MRI reading and reporting. The Mayo-ADIR Clinic will review MRIs and provide a report on ARIA-E and ARIA-H. This report will include both definite and possible findings. A report of new definite ARIA changes in a participant will trigger a review by the Medical Director or designee, PAL, and site principal investigator or delegated sub-investigator. The site principal investigator or designated sub-investigator, in conjunction with the appropriate PAL and the DIAN-TU Medical Director or designee, will review new ARIA findings and apply the intervention algorithms below using best clinical judgment to weigh the data available to decide whether changes in drug treatment are indicated.

ARIA-related intervention algorithm

The tables below detail the ARIA-E linked intervention algorithm based on these scores (Table 1 and Table 2) and the intervention algorithm for ARIA-H microhemorrhage (Table 3) and superficial siderosis (Table 4). Algorithms are based on definite ARIA findings only. For ARIA-E, the algorithm relies on measures of the largest diameter of any ARIA-E. For ARIA-H, areas of microhemorrhage are counted and larger areas of hemorrhage (macrohemorrhage) are noted. Should both ARIA-E and ARIA-H be present in the same participant, the more conservative procedure should be followed.

For ARIA cases where there are symptoms that are possibly related to the ARIA findings, more stringent procedures should be considered (e.g., withhold treatment for symptomatic cases even if the procedures in the table would not require it).

Table 1 Procedures for Asymptomatic ARIA-E

Number of New Occurrences¹	Dose Adjustment	MRI Monitoring
Any new individual lesions ≤ 2 cm	Continue current dose; do NOT titrate up. If stable or decreased on subsequent MRI, continue study drug at the same dose but do NOT titrate up. Once resolved, up titration may resume. An appropriate dosage may be resumed based on discussion between the site PI or designated sub-investigator, PAL, and Medical Director or designee, at minimum.	Every 4 weeks until resolved

Number of New Occurrences ¹	Dose Adjustment	MRI Monitoring
Any new individual lesions > 2 cm	Follow the Symptomatic ARIA-E guidance.	Follow the Symptomatic ARIA-E guidance

¹ Based on new definite ARIA findings (excluding baseline incidences)

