Table 2 Procedures for Symptomatic ARIA-E: Any incidence of symptomatic ARIA-E or asymptomatic with lesions >2 cm

Step-wise Response	Dose Adjustment	MRI Monitoring
Initial action	Suspend/hold dosing.	Every 4 weeks until resolved
Once symptoms and ARIA-E resolve	Restart study drug at an appropriate dosage based on discussion between the site PI or designated sub-investigator, PAL, and Medical Director or designee, at minimum.	4 weeks after dosing restart
If no new MRI findings after dosing restart and MRI	Resume up titration per protocol. An appropriate dosage may be resumed based on discussion between the site PI or designated sub-investigator, PAL, and Medical Director or designee, at minimum.	Resume MRI monitoring per protocol

Note: Asymptomatic lesions > 2 cm are based on measurements of new definite ARIA findings

Table 3 Procedures for ARIA-H Microhemorrhage

Number of New Occurrences¹	Dose Adjustment	MRI Monitoring
5-9 new, cumulative occurrences ²	Continue current dose and titration schedule.	MRI 4 weeks later then continue MRI monitoring per protocol
10-15 new, cumulative occurrences	Suspend/hold dosing until stable upon MRI. An appropriate dosage may be resumed based on discussion between the site PI or designated sub-investigator, PAL, and Medical Director or designee, at minimum.	Every 4 weeks until stable
>15 new, cumulative occurrences	A dosing and safety monitoring plan for the participant to be developed by the Site PI, PAL, and Medical Director or their designees based on a thorough safety review. If dosing is discontinued, the participant will be encouraged to complete other assessments and visits per protocol.	MRI 4 weeks later with further MRI monitoring based on the safety monitoring plan developed for the participant

¹ Based on new definite ARIA findings (excluding baseline incidences)

² MRI 4 weeks after each new occurrence between 2-4 microhemorrhages, i.e., 2, 2 to 3, 3 to 4.

Table 4 Procedures for Superficial Siderosis

Number of New Occurrences¹	Dose Adjustment	MRI Monitoring
1 new occurrence of superficial siderosis	Continue dosing at the participant's current dose; do NOT titrate up.	MRI 4 weeks later then continue MRI monitoring per protocol

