2-3 new occurrences of superficial siderosis	Stop/hold dosing until MRI 4 weeks later. If additional MRI shows no new lesions, an appropriate dosage and MRI monitoring frequency may be resumed based on discussion between site PI or designated sub-investigator, PAL, and Medical Director or designee, at minimum.	MRI 4 weeks later then continue MRI monitoring per protocol
> 3 new occurrences of superficial siderosis	Consider discontinuation of dosing for the remainder of the trial but continue participation and completion of other assessments and visits per protocol.	MRI 4 weeks later with further MRI monitoring per the safety monitoring plan developed for the participant

¹ Based on new definite ARIA findings (excluding baseline incidences)

ARIAs may be reported as an AE per MedDRA-preferred term based upon investigator's discretion upon review of the MRI finding, assessment of clinical symptoms, and adverse event definitions as outlined in Section 7.1.1.

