18.3. SAFETY MRI EVALUATIONS

The number and percentage of subjects with MRI scan (including annual, safety, and dose titration MRIs) conducted will be summarized by visit for each type of MRI finding during the OLE. Summaries will also display the number of subjects with a new finding and those with any post-baseline finding for each type of MRI finding.

ARIA can occur as either cerebral edema (ARIA-E) or as hemorrhages (ARIA-H), typically microhemorrhages, but larger hemorrhages and frank infarction have also been reported. MRI scans will be analyzed for ARIA changes at the Mayo Clinic Aging and Dementia Imaging Laboratory. The number of microhemorrhages (ARIA-H, including both hemorrhages and hemosiderin deposits) and size of areas of edema (ARIA-E) will be monitored at entry and throughout the trial.

Frequencies and percentages of ARIA-E will be summarized by dose (all doses), by visit, and for the highest post-baseline value. Frequency and percentage of ARIA-H will be summarized by dose separately for ARIA-H Microhemorrhages and ARIA-H Superficial Siderosis, with summarizes separated for those associated with ARIA-E and those which are not. The number of ARIA-H and ARIA-E will be categorized (1, 2 to 4, 5+, or no presence). The size of ARIA-E, where present, will be summarized using mean (SD) by visit. A summary of time to ARIA-E resolution will be presented. ARIA-E resolution corresponds to the first MRI following a new post-baseline ARIA-E finding where no definite findings are observed and is calculated as the date of the MRI with no findings – the date of the MRI with AREA-E +1 day. If a subject has

Author: [REDACTED]

Version Number:

7

Version Date:

07Dec2023

Template No.: CS_TP_BS016 Revision 6

Reference: CS_WI_BS005

Effective Date: 02Dec2019

more than one ARIA-E that resolves, the largest duration per subject will be used for the summary of time to ARIA-E resolution. A listing of all ARIA-E findings will be produced for all subjects who have an incidence of ARIA-E at any assessment. The listing will include the number of definite findings for ARIA-E, the size of ARIA-E, the number of days since treatment start, the current active drug dose, and the number of days since start of the current active drug dose. In addition, the frequencies and percentages of the following findings will be summarized in separate tables by visit and for the highest post-baseline value:

- Large cortical infarctions
- Small cortical infarctions

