- Subcortical infarctions
- Acute ischemia infarctions
- Other findings (frequencies and percentages only, including for individual sub-categories)

MRI findings will be listed. Details for other findings will be listed separately for all subject with other MRI findings at any assessment. The listing will include number of definite other findings, a description of the other findings, number of days since treatment start, current active dose and the number of days since start of the current active dose.

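### SAP 18.3's ARIA count categories do not separate the protocol's upper ARIA-H action tiers, and no planned table shows the ARIA-E size-or-symptom trigger

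*SAP*

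**What the plan says.** **SAP, Section 18.3.** One set of count categories serves all ARIA: "The number of ARIA-H and ARIA-E will be categorized (1, 2 to 4, 5+, or no presence". Microhemorrhage and siderosis are kept apart: "Frequency and percentage of ARIA-H will be summarized by dose separately for ARIA-H Microhemorrhages and ARIA-H Superficial Siderosis". ARIA-E frequencies are given by dose, by visit and for the highest post-baseline value. Lesion size has one summary: "The size of ARIA-E, where present, will be summarized using mean (SD) by visit". Participants with a new finding, and with any post-baseline finding, are also counted.

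There are two relevant listings. The ARIA-E listing includes "the number of definite findings for ARIA-E, the size of ARIA-E, the number of days since treatment start, the current active drug dose". For everything else the plan says only "MRI findings will be listed".

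**Protocol Appendix 3, Section 1.14.** Table 3 sets three microhemorrhage rows, the middle one being "10-15 new, cumulative occurrences". Table 4 sets three siderosis rows, the top one being "> 3 new occurrences of superficial siderosis". Both tables use new definite findings with baseline findings left out. For ARIA-E, "the algorithm relies on measures of the largest diameter of any ARIA-E", with 2 cm as the dividing line in Tables 1 and 2. Symptomatic ARIA-E of any size is handled with the larger lesions.

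**The concern.** Safety and tolerability at higher doses is a primary endpoint of the open-label extension (Protocol Appendix 3, Section 1.9.2), with particular attention to ARIA (Section 1.11). The double-blind target was 1200 mg every 4 weeks and the extension goes up to 1500 mg every 2 weeks. The nominal amount per 4 weeks therefore rises from 1200 mg to 2 × 1500 = 3000 mg. A reader of the report will want to know how many participants reached the ARIA levels at which the protocol holds or reconsiders dosing, and at what dose.

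The SAP's categories were not drawn at those levels. A participant with 5 new microhemorrhages, for whom dose and titration go on unchanged, shares a cell with one who has 16, for whom an individual dosing and safety plan is made.

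**Working it through.** The documents give no figure to reproduce here. The check is a cross-mapping of the two sets of cut-points.

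**Inputs.** SAP categories 0, 1, 2-4, 5+ (SAP 18.3). Protocol tiers from Appendix 3, Tables 3 and 4, including footnote 2 to Table 3, which covers counts of 2-4.

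**Rule.** A threshold can be read from the table only if no SAP category holds counts on both sides of it.

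| SAP category | Microhemorrhage tier (Table 3) | Siderosis tier (Table 4) |
|---|---|---|
| 0 | none | none |
| 1 | none | 1: dosing goes on, no up-titration |
| 2-4 | 2-4: extra MRI, no dose action | 2-3: hold; 4: consider discontinuation |
| 5+ | 5-9: unchanged; 10-15: hold; above 15: individual plan | 5 or more: consider discontinuation |

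**Results.**
- Microhemorrhage ≥10: '5+' holds 5-9 (below) and 10 upward (above). Not readable.
- Microhemorrhage >15: '5+' holds 5-15 (below) and 16 upward (above). Not readable.
- Siderosis ≥2: 0 and 1 lie below; '2-4' and '5+' lie wholly above. Readable as the sum of those two cells.
- Siderosis >3: '2-4' holds 2 and 3 (below) and 4 (above). Not readable.

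Three of the four fail and one passes. At the lower end of Table 3 the '2-4' category and the cut at 5 agree with the protocol.

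**What the cells still bound.** Suppose the categories count new cumulative findings. Then the number with microhemorrhage ≥10 lies between 0 and the '5+' count. The number with siderosis >3 lies between the '5+' count and the sum of '2-4' and '5+'. If the '5+' microhemorrhage cell is empty, the answer is zero and nothing is lost. The SAP does not state the counting basis. If it counts all findings on a scan, baseline included, even the siderosis ≥2 sum does not match the protocol's tier.

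**ARIA-E.** The action depends on diameter or symptoms, so no grouping by number of lesions can show it. A mean and SD do not fix how many values exceed 2 cm. The size summary is also by visit rather than dose, and visit is an imperfect stand-in for dose: Appendix 3, Section 2.2 allows participants to be out of step with the scheduled weeks. Section 18.3 plans no table of symptomatic ARIA-E.

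**Other outputs.** The adverse event overview (SAP 18.1) has rows for treatment and study discontinuation but none for dose holds. Recording ARIA as an adverse event is left to the investigator (end of Appendix 3, Section 1.14), and no events of special interest are defined (Appendix 3, Section 5). The exposure tables (SAP 15) give duration, doses and compliance without a reason for missed doses. For ARIA-H, the listing sentence names neither a dose column nor a cumulative count of new findings.

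**The case against.** Several points on the other side are sound.

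- **The information is not lost.** The ARIA-E listing carries size and current dose for each finding, so the 2 cm split can be made by hand. With a recruitment goal of 60 to 90 (Appendix 3, Section 4.1.2), that is feasible. A reader might infer that the split disappears altogether; it is absent only from the tables.
- **The categories are not arbitrary.** They agree with the lower part of Table 3, and 5+ also appears as a microhemorrhage cut in SAP Table A. A reader might infer that the tables show nothing about hold-level ARIA-H, but siderosis ≥2 can be read on the stated condition.
- **A tier is not a dose hold.** Section 1.14 leaves room for clinical judgment, for the more conservative procedure when both ARIA types are present, and for stricter handling of symptoms. Above 15 microhemorrhages the protocol calls for an individual plan, and above 3 siderosis findings it asks that discontinuation be considered. Neither is automatic discontinuation.
- **Dosing consequences appear elsewhere in part.** Drug administration is listed, and adverse events leading to treatment termination are listed. Main protocol Section 7.1.1 calls for abnormal tests that change dosing to be recorded as adverse events, though this sits uneasily with the discretion given for ARIA.
- **No passage requires the tables to mirror the algorithm.** The output templates (SAP 8) and the separate DSMB plan (SAP 4.1) are not among the documents, and the report is to be abbreviated after early termination. Nothing shows that the upper tiers will be populated.

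These points limit the size of the gap. They do not close it, because no output described in the SAP tabulates the upper ARIA-H tiers or the ARIA-E trigger.

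**Conclusion.** The point stands as a reporting gap. As described in SAP 18.3, the summary tables cannot give the number of participants with microhemorrhage ≥10 or >15, with siderosis >3, or meeting the ARIA-E trigger of symptoms or more than 2 cm. Siderosis ≥2 can be recovered if new findings are counted.

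This assumes that the unseen table templates follow the text of Section 18.3, and that the listed ARIA-E size is the largest diameter. The practical size depends on how many participants fall in the pooled cells, which the documents do not tell.

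A reader might infer that participants are less well protected. The documents do not support that: the intervention algorithm, the sentinel cohorts, Medical Monitor review and quarterly DSMB review all run independently of these tables. It would be equally wrong to read tier counts, once tabulated, as counts of doses actually held.

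**What to change.** In SAP 18.3, replace the single scale with the protocol's own tiers, presented by dose and for the highest post-baseline value, counting new definite cumulative findings with baseline findings excluded:

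- Microhemorrhage: 0, 1, 2-4, 5-9, 10-15, >15.
- Superficial siderosis: 0, 1, 2-3, >3.
- ARIA-E: none; asymptomatic with largest diameter ≤2 cm; symptomatic or >2 cm. Keep the mean (SD) of size beside it. A split on size alone would miscount the trigger, because symptoms count at any size.

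State the counting basis, including which baseline is meant, since the protocol does not name it, and how a cumulative count is assigned to a dose. Add a footnote that tiers describe findings and not dosing decisions.

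**Cost.** Counts and sizes are already collected, and no model, endpoint or management rule changes. Cells will be sparse, although an empty upper tier is itself useful to report. ARIA-E symptom status may have to be linked from clinical or adverse event data, which is the only part that might need new programming beyond regrouping.

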			
the interim analysis, will be conducted much earlier than the original timeline. As a result, the external dataset DF17, which was planned to be used for the final analysis, will not be available on time. To avoid further delays in the final analysis, the same external dataset DF16 will be used for the final analysis as well.
 
3. Reallocate certain secondary efficacy endpoints (initially listed in the no longer present section 16.2.1.2) as exploratory endpoints (now detailed in section 16.3).
 
Rationale for this change: The interim analysis resulted in the early termination of the OLE study without a path for regulatory approval. Consequently, several secondary efficacy endpoints are not relevant and the final Clinical Study Report (CSR) will be abbreviated.
 
In summary, these modifications do not impact any of the pre-specified statistical models outlined in this SAP, nor do they alter any primary or key secondary endpoints. They address challenges stemming from the pandemic and the premature termination of the OLE study. Consequently, they will not compromise the overall integrity of the trial.
 
4. Update Columbia Suicide Severity Rating Scale description and analysis (sections 12, 18.7.1) according to CRF.

Author: [REDACTED]

Version Number:

7

Version Date:

07Dec2023

Template No.: CS_TP_BS016 Revision 6

Reference: CS_WI_BS005

Effective Date: 02Dec2019

TABLE OF CONTENTS

1. INTRODUCTION.....	14
2. STUDY OBJECTIVES.....	14
2.1. PRIMARY OBJECTIVE	14
2.2. SECONDARY OBJECTIVES.....	14
[REDACTED]	
2.4. SAFETY OBJECTIVES.....	16
3. STUDY DESIGN.....	16
3.1. GENERAL DESCRIPTION	16
3.2. SCHEDULE OF EVENTS.....	17
3.3. CHANGES TO ANALYSIS FROM PROTOCOL	17
4. PLANNED ANALYSES	18
4.1. DATA SAFETY MONITORING BOARD (DSMB).....	18
4.2. FINAL ANALYSIS	18
4.3. INTERIM ANALYSIS	19
5. ANALYSIS SETS.....	19
5.1. PROCESS FOR ANALYSIS SET ASSIGNMENT	20
5.2. ALL SUBJECTS ENROLLED SET [ENR]	20
5.3. MODIFIED INTENT-TO-TREAT [MITT]	20
5.4. GROUPS OF CONTROLS.....	23
5.4.1. EXTERNAL CONTROLS.....	23
5.4.2. INTERNAL SET CONTROLS	26
5.4.3. MAIN SET CONTROLS	26

Author: [REDACTED]

Version Number:

7

Version Date:

07Dec2023

Template No.: CS_TP_BS016 Revision 6

Reference: CS_WI_BS005

Effective Date: 02Dec2019

5.4.4. EXTENDED SET CONTROLS.....	26
5.4.5. CONCURRENT CONTROLS	26
5.4.6. CONTROLS APPLIED TO INDIVIDUAL ANALYSIS POPULATIONS	27
5.5. SAFETY ANALYSIS SET [SAF]	27
6. GENERAL CONSIDERATIONS.....	27

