7.3. MISSING DATA

There will be no imputation of missing data. Handling of missing data for specific efficacy endpoints is detailed in [Sections 16.1.2](#) and [16.2.2](#).

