16.2.3.2. Primary Analysis of CDR Global

The primary analysis will be on the All Gant Exposure mITT, with all the other baseline covariates (such as baseline EYO) defined in the same way as baseline for the associated population. The time to the first disease progression is defined as the time from the baseline to the first visit where CDR Global is greater than CDR Global baseline value, where a progression is considered an increase above baseline observed at two consecutive measurements unless the progression occurs at the last measurement. Subject without progression will be censored at their last measurement.

The Cox proportional hazards model will be applied to compare the hazards of disease progression in CDR Global between each of the three mITT population separately and all

Author: [REDACTED]

Version Number:

7

Version Date:

07Dec2023

Template No.: CS_TP_BS016 Revision 6

Reference: CS_WI_BS005

Effective Date: 02Dec2019

controls. The models will include the treatment group (specifically gantenerumab and controls) and baseline EYO as the fixed effects.

Analyses will be conducted separately for baseline asymptomatic and symptomatic subjects. A Kaplan-Meier figure will be generated for baseline asymptomatic subjects for all three mITT populations and associated controls.

Spaghetti plot of EYO for each participant will be presented for each of the three mITT populations. Lines and data points will be coded by different color/symbol for different CDR groups (without progression, with progression) and doses. This figure will be generated by Washington University team.

16.2.3.3. Primary Analysis of OLE Cognitive Composite, FAS, MMSE, Tau-PET SUV, CSF NfL and CSF MTBR243

The annual disease progression between the OLE Gant mITT population and all controls (with the exception of internal controls only for Tau-PET SUV) will be compared using a linear mixed effects (LME) model. CSF NfL will be log transformed for the analysis. The LME model will include time since baseline (in years: treated as continuous), treatment group (the OLE Gant mITT and all control), interaction between the treatment group and time, and random intercepts and slopes for each subject as the random effects. The unstructured covariance will be used to model the covariance between random intercepts and random slopes and will be modelled separately for baseline asymptomatic and symptomatic subjects.

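### SAP 18.3 leaves ARIA-E episodes still open at the last MRI out of the time-to-resolution summary; the omission alone biases the duration downward, but the net direction is unknown

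*SAP*

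**What the plan says.** SAP Section 18.3 plans the summary in one sentence: "A summary of time to ARIA-E resolution will be presented". It names no statistic or estimator. The end of an episode is defined: "ARIA-E resolution corresponds to the first MRI following a new post-baseline ARIA-E finding where no definite findings are observed". The duration is the date of that clearing MRI minus the date of the MRI showing ARIA-E, plus 1 day. Repeat episodes have a rule. Where a participant has "more than one ARIA-E that resolves, the largest duration per subject will be used for the summary of time to ARIA-E resolution".

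No rule covers an episode without a clearing MRI. SAP Section 7.3 adds that "There will be no imputation of missing data", so no end date is created for it. The SAP does handle incomplete follow-up for other times to event. For CDR Global, Section 16.2.3.2 states: "Subject without progression will be censored at their last measurement".

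Other outputs in Section 18.3 do not depend on resolution. They include ARIA-E frequencies by dose, by visit and at the highest post-baseline value, and size by visit. In addition, "A listing of all ARIA-E findings will be produced for all subjects who have an incidence of ARIA-E at any assessment".

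**The concern.** The summary conditions on the outcome it measures: only episodes seen to end can contribute. At any given point where MRI follow-up stops, longer episodes are more likely to be still open, so keeping only the resolved ones favours the shorter ones. A participant whose only episode never cleared disappears from the summary. One with a short resolved episode and a longer open one is represented by the short one, although the largest-duration rule seems meant to show the worst case.

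Open episodes are plausible. The version 7 entry in the SAP history says: "The interim analysis resulted in the early termination of the OLE study without a path for regulatory approval". Protocol Appendix 3, Section 1.4 reports that 3 of 10 double-blind ARIA-E cases discontinued, and the safety follow-up visit in Section 3.2.7 lists no MRI.

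At stake is how the duration of a main safety risk is described. The Risks/Benefits text (Appendix 3, Section 1.6) already cites the double-blind version of this statistic, and the OLE uses higher doses.

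**Working it through.** The documents give no expected OLE duration, sample size or precision for this summary, so there is no design figure to reproduce. What follows is an illustration.

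**Inputs from the documents**
- Double-blind time to resolution: mean 10.4, SD 6.2 weeks (Protocol Appendix 3, Section 1.6).
- Double-blind incidence: 10/52 = 19.2% (Sections 1.5.2.3 and 1.6). Section 1.4 prints the same percentage with denominator 48, but 10/48 = 20.8%, so 52 is used here.
- OLE size: 60 to 90 (Section 4.1.2).

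**Assumptions not in the documents**
- Durations follow a gamma distribution with that mean and SD: shape (10.4/6.2)² = 2.81, scale 6.2²/10.4 = 3.70 weeks (400,000 draws).
- MRI follow-up stops early in 10% to 50% of participants with ARIA-E (100% as an extreme), uniformly over 0 to 16 weeks after onset and independently of duration.
- 0% to 30% of these participants have a second episode.

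**Step 1: number of cases.** 60 × 10/52 = 11.5 and 90 × 10/52 = 17.3, so about 12 to 17. One unresolved episode in 17.3 is 6%; two in 11.5 is 17%.

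**Step 2: omission alone.** If T is the duration and C the time at which follow-up stops, the resolved episodes have density proportional to f(t) × P(C ≥ t). The second factor falls with t, so the resolved-only distribution is shifted towards shorter values.

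| Follow-up stops early | Unresolved | Resolved-only mean (weeks) | Resolved-only median | Kaplan-Meier median |
|---|---|---|---|---|
| 0% | 0% | 10.4 | 9.2 | 9.2 |
| 10% | 6% | 10.2 | 9.0 | 9.2 |
| 20% | 12% | 10.0 | 8.8 | 9.2 |
| 30% | 18% | 9.8 | 8.6 | 9.2 |
| 50% | 30% | 9.3 | 8.1 | 9.2 |
| 100% | 60% | 6.4 | 6.1 | 9.2 |

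**Step 3: largest-per-participant rule alone.** With every episode resolved and 0%, 10%, 20% or 30% of participants having a second one, the mean of the per-participant maximum is 10.4, 10.7, 11.1 or 11.4 weeks. This pushes upward.

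**Step 4: both together.** Early stopping is applied to the participant's last episode. With 20% stopping early, the mean under the SAP rule is 10.0, 10.4, 10.7 and 11.0 weeks for 0%, 10%, 20% and 30% recurrence. Over early stopping of 10% to 30% and recurrence of 0% to 30%, it runs from 9.8 to 11.2 weeks, on either side of the true 10.4.

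**Step 5: MRI grid.** Dating resolution at the next 4-weekly MRI raises the mean from 10.4 to 12.4 weeks, about 2 weeks, if onset is dated exactly. Late detection of onset works the other way.

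**The case against.** The strongest reply is that the documents do not show a single unresolved OLE episode, and that the protocol works to prevent them. Appendix 3, Section 1.14 sets MRI monitoring for ARIA-E as "Every 4 weeks until resolved". The early termination visit (Section 3.2.8) is meant to repeat the OLE Visit 40 procedures, which include an MRI with safety sequences. Main protocol Section 7.5 follows adverse events until they resolve or are judged stable, chronic or not clinically significant. Termination followed an interim timed for Year 2 data, while titration takes about 15 months, so many episodes may have begun well before follow-up ended. All of this stands and limits the likely loss. It does not tell the programmer what to do when a clearing scan is missing.

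A second reply is that nothing is hidden, because the listing and frequency tables include every affected participant. That is true of occurrence. But the listing fields named in Section 18.3 include neither resolution status nor duration, so a reader would have to rebuild both scan by scan. The table templates mentioned in SAP Section 8 are not in the text available here and might carry a count of unresolved episodes; this could not be checked.

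A third reply is that the quoted rule itself lengthens the summary. This also stands (Steps 3 and 4). It does not repair the omission: the rule changes nothing for a participant with one episode, and any cancellation depends on an unknown recurrence rate.

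A reader might go further and infer that the reported duration is too short, or that the longest episodes are removed. The documents do not support either. An episode first seen on the last MRI is open without being known to be long, and the two upward effects can outweigh the omission. A constant-rate calculation with a sizeable share of episodes open at a late date would suggest a large shortening, but those inputs would be invented. A constant rate also implies an SD equal to the mean, whereas the double-blind figures are 6.2 and 10.4 weeks.

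**Conclusion.** The point holds in a limited form. Followed as written, SAP 18.3 excludes any ARIA-E episode unresolved at the last MRI and picks the largest duration only among resolved episodes. The exclusion follows from the definition together with the no-imputation rule; the SAP does not state it outright. Taken alone, the omission biases the duration downward when stopping of follow-up is unrelated to duration. Under the assumptions above, the median is understated by about 0.2 to 1.1 weeks (9.2 against 9.0 to 8.1) when 6% to 30% of episodes are unresolved. The net direction and size for the actual table are unknown.

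This affects a descriptive safety summary of perhaps 12 to 17 cases. It affects no primary or key secondary analysis. The change is worth making because the present rule conditions on the outcome and the standard replacement is cheap.

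**What to change.** Revise the time-to-resolution paragraph in SAP 18.3 as follows:

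- Report the number of participants and the number of episodes unresolved at the last MRI.
- Summarise time to resolution by Kaplan-Meier, with the median and 95% CI, censoring unresolved episodes at the last MRI.
- Use one prespecified episode per participant, for example the first new post-baseline episode. If all episodes are kept, use a confidence interval that allows for repeat episodes within a participant, such as a bootstrap that resamples participants.
- Keep the largest resolved duration per participant, if wanted, as a supplementary line labelled as resolved episodes only.

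Kaplan-Meier does not remove the MRI-grid effect in Step 5, so a footnote should say that resolution is dated at the first clearing MRI. If the SAP can no longer be amended, its Section 6 allows the change to be documented as a deviation in the CSR.

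The cost is some SAP wording and one revised table. The reported duration may come out longer, and with so few cases the interval will be wide. If no episode is unresolved, the added line reads zero and the table is easier to interpret.
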